2.2.5 Risks and Benefits

This is a Phase I exploratory study in healthy male and female volunteers.

HIV DNA plasmid-based vaccines are widely used alone and in combination regimens, including the multicentre EuroVacc trials EV01-3 in which we have been involved and which volunteers were given up to 12mg DNA over 12 weeks with no safety concerns. There is currently limited data available on the systemic use of CN54ENV DNA but our group is directly involved in the only trial using CN54ENV and CN54gp140 delivered IM in DNA-MVA-protein strategy (UKHVC SPOKE 003; EUDRACT: 2012-003277-26) initiated in July 2013 and now completed, for which our group have direct access to safety data as it becomes available.

While electroporation has been used in multiple studies, it has not been used to deliver this particular vaccine in humans before, but the supporting preclinical study (CR 525569), was shown to be well tolerated in rabbits. Furthermore, a previous Phase I trial to use electroporation (EP) for the delivery of a DNA vaccine for HIV demonstrated increased immunogenicity in the absence of associated safety concerns [44] [62]. A more recent study (HVTN 080) assessed a mixture of 3 expression plasmids encoding HIV-1 Clade B Env, Gag, and Pol delivered together with a DNA expressing IL-12 followed by EP with no associated safety concerns [63]). The vaccination schedules in this study are complex and on each visit volunteers will receive at least one vaccination with EP. There is an increased risk that retention to the trial will suffer as a result. The first Phase I trial to use EP for the delivery of a DNA vaccine for HIV has recently reported and observed an increase in immunogenicity. All the volunteers completed their immunisations, and adverse reactions were in line with licensed vaccines. In the ongoing healthy volunteer study (CUTHIVAC 001, EUDRACT 2011-003171-11), one participant elected to discontinue further immunisations due to pain and eight participants were subsequently randomised to EP and preceded without a problem.

There is no direct benefit to the volunteers. They will be reimbursed for their time and travel. Volunteers also derive the benefits of clinical screening and any follow up care for the time that they are enrolled in the study and afterwards where appropriate. As there is no placebo group, there is a risk that adverse events will be over-reported, but this should not influence grade and is not a concern at this stage of evaluation.

The laboratory endpoints will be analysed in laboratories at Imperial College London, and the staff blinded to the regimen, although not the time point. Samples may also be shipped to specialist laboratories in Europe and the USA for wider exploratory immunological measurements of interest. Procedures will be put in place to ensure the chain of custody of samples when transporting from clinic to laboratory and between laboratories; therefore we consider that the risk of loss or compromise of samples is low.

3. SELECTION OF CENTRES/CLINICIANS

The Principal Investigator, [name] (Imperial Clinical Research Facility, Hammersmith Hospital) is an experienced clinical trialist. Volunteers will be seen by clinical staff from the Imperial Clinical Research Facility, Imperial College Healthcare NHS Trust, who have experience of running Phase 1 clinical trials.

4. SELECTION OF PARTICIPANTS

There will be **no exceptions** to eligibility requirements at the time of randomisation. Questions about eligibility should be addressed prior to attempting to randomise the participant.

The eligibility criteria for this trial have been carefully considered. The eligibility criteria are the standards used to ensure that only appropriate participants are considered for this study. Participants not meeting the criteria should not join the study. For the safety of the participants it is important that no exceptions be made to these criteria for admission to the study.

Participants will be considered eligible for enrolment in this trial if they fulfil all the inclusion criteria and none of the exclusion criteria as defined below.

4.1 Participant Inclusion Criteria

1. Men and women aged between 18 and 50 years (inclusive) on the day of screening
2. BMI between 18-30 kg/m² (inclusive)
3. Available for follow-up for the duration of the study (up to ~12 months from screening)
4. Willing and able to give written informed consent
5. At low risk of HIV and willing to remain so for the duration of the study defined as:
 - no history of injecting drug use in the previous ten years
 - no gonorrhoea or syphilis in the last six months
 - no high risk partner (e.g. injecting drug use, HIV positive partner) either currently or within the past six months
 - no unprotected anal intercourse in the last six months, outside a relationship with a regular partner known to be HIV negative
 - no unprotected vaginal intercourse in the last six months outside a relationship with a regular known/presumed HIV negative partner
6. Willing to undergo a HIV test
7. Willing to undergo a genital infection screen
8. Must agree to require male sexual partner to use condoms, from at least 14 days before the first vaccination until at least 4 months after the last
9. If heterosexually active female capable of becoming pregnant, must (in addition to requiring male partner to use condoms) agree to use hormonal contraception, or to

complete abstinence, from at least 14 days before the first vaccination until at least 4 months after the last. [Note: Periodic abstinence (e.g. calendar, ovulation, symptothermal, post-ovulation methods) and withdrawal, and IUD/IUS, are not acceptable methods of contraception.] If sexually active male, must agree to use condoms from the day of first vaccination until at least 4 months after the last. [Note: Additional use of an effective method of contraception is recommended for any non-pregnant female partner over the same period.]

10. Agree to abstain from donating blood for three months after the end of their participation in the trial, or longer if necessary
11. Registered with a GP for at least the past three months
12. Entered and clearance obtained from The Over-volunteering Prevention System (TOPS) database.

4.2 Participant Exclusion Criteria

1. Pregnant or lactating
2. History of cardiac arrhythmia or palpitations [e.g., supraventricular tachycardia, atrial fibrillation, frequent ectopy, or sinus bradycardia prior to study entry (sinus arrhythmia is not excluded)]
3. History of syncope or fainting episodes within 1 year of study entry
4. History of grand-mal epilepsy, seizure disorder or any history of prior seizure
5. Individuals in which a skin-fold measurement (cutaneous and subcutaneous tissue) of the upper right and left thigh exceeds 40 mm
6. Clinically relevant abnormality on history or examination
7. Known hypersensitivity to any component of the vaccine formulations used in this trial, or have severe or multiple allergies to drugs or pharmaceutical agents
8. History of severe local or general reaction to vaccination defined as
 - local: extensive, indurated redness and swelling involving most of the antero-lateral thigh or the major circumference of the arm, not resolving within 72 hours
 - general: fever $\geq 39.5^{\circ}\text{C}$ within 48 hours; anaphylaxis; bronchospasm; laryngeal oedema; collapse; convulsions or encephalopathy within 72 hours
9. Receipt of live attenuated vaccine within 60 days or other vaccines within 14 days of enrolment
10. Receipt of an experimental vaccine containing HIV envelope components at any time in the past
11. Receipt of blood products or immunoglobulin within 4 months of screening
- 12.
13. Has received treatment with immunosuppressive agents within 3 months of screening e.g. oral, inhaled, nasal or injected corticosteroids. (Topical steroids are allowed, unless applied to the IM or ID injection sites.) Participation in another trial of a medicinal product, completed less than 30 days prior to enrolment.
14. HIV 1 or 2 positive or indeterminate on screening.

15. Positive for hepatitis B surface antigen, hepatitis C antibody or serology indicating active syphilis requiring treatment
16. Grade 1 (or above) clinically significant routine laboratory parameters (see appendix 2 for definitions). Hyperbilirubinaemia to be considered an exclusion criterion only when confirmed to be conjugated bilirubinaemia
17. Current use of any electronic stimulation device, such as cardiac demand pacemakers, automatic implantable cardiac defibrillator, nerve stimulators, or deep brain stimulators.
18. Presence of any surgical or traumatic metal implants at the sites of administration
19. Unable to read and speak English to a fluency level adequate for the full comprehension of procedures required in participation and consent.
20. Women with a history of toxic shock syndrome.
21. Women using an intrauterine device for contraception (as incompatible with softcup sampling)
22. Unlikely to comply with protocol.

4.3 Number and Source of Participants

Healthy volunteers will be recruited through advertising. They will be provided with further information about the study and asked to complete a short interview (by telephone or in person) to assess their suitability. They will be given or sent an information sheet. The target is for 24 participants to complete the trial.

4.4 Screening Procedures and Pre-Randomisation Investigations

At the screening visit the volunteer will be allocated a number from the register. The trial will be discussed in detail, and a brief check of eligibility conducted. Any questions about the study will be answered. If volunteers appear potentially eligible, and willing and interested, they will be asked to sign the informed consent form.

After written informed consent has been collected, assessments and investigations will be undertaken according to the schedule in **Table 5 , section 7**. These include demographic, sexual and medical histories and general examination, and collection of urine and blood samples for routine laboratory investigations. Samples for screening sexually transmitted infections including HIV will be collected (**see section 7.2**). An ECG will be performed.

As soon as all required test results are available:

- Data will be entered onto the screening CRF and the results of the screening investigations will be reviewed and eligibility signed off by a physician.

5. RANDOMISATION & ENROLMENT PROCEDURE

5.1 Randomisation Practicalities

The enrolment visit will take place within 6 weeks (42 days) of the screening visit and will be the same day as the first vaccination. Assessments and procedures will be undertaken according to the schedules (**Section 7** and **Table 5**), and data entered on the case report forms.

Volunteers who are eligible and willing will be randomised when all inclusion/exclusion criteria have been met and the appropriate CRF completed. The PI or team member will log into a web-based system managed by MRC CTU at UCL to obtain the regimen allocated to the participant.

Further details on the process of randomisation can be found in **Section 10**.

5.2 Randomisation Codes and Un-blinding

The master randomisation list linking subject numbers to allocation will be generated by the trial statistician. Randomisation will be carried out on the day of the first dosing visit.

Randomisation arm will be known to participants and clinical staff.

The laboratory staff conducting the assays will be blind to the regimen throughout.

The trial is open-label so no unblinding will be necessary.

5.3 Co-Enrolment Guidelines

Participants will be advised that they cannot enrol in any other trials that would interfere with the study endpoints during the period from screening to the final visit in CUTHIVAC002. All participants will be entered onto the TOPS (The Overvolunteering Prevention System) database as a measure to prevent over volunteering.

If staff discover that a participant is enrolled on another study during this period, they must immediately contact the Chief Investigator for advice. Decisions will be reviewed on a case by case basis and participant safety will be the primary concern.

6. TREATMENT OF PARTICIPANTS

6.1 Vaccine Products

Participants will be vaccinated in a schedule of doses and methods as described below. Each participant will receive three DNA immunisations, at wk 0, 4 and 8, boosted with recombinant HIV CN54gp140 administered by intradermal injection at wk 20.

A vaccine accountability log will be kept throughout the study. This should be used to record the Trial ID of the subject to whom the study vaccine was dispensed. This will be verified by the study monitor. The date and time of administration will be recorded on the CRF.

6.1.1 Products and Administration

The individual IMP vials will be labelled, and packaged in cartons which will also be labelled. The Principal Investigator will ensure that staff administering the vaccines have been appropriately trained in the written procedures for ID, IM and EP.

All individuals will be given one IM injection of 2.0mg CN54ENV DNA and one ID injection of 0.6mg of CN54ENV DNA at Weeks 0, 4 and 8, and one ID injection of 50 µg CN54gp140 at Week 20. See table 1, section 6.1.3.

6.1.2 Accountability for Used and Unused Supplies

The PI will ensure that the IMPs are dispensed in accordance with the protocol and local procedures, and that records are maintained of receipt, dispensing and return/destruction of all supplies.

The PI must ensure that all IMP supplies are kept in a secure area accessible only to authorised individuals, and maintained in storage that guarantees the following temperatures:

- CN54ENV DNA at -25 to -15°C
- CN54gp140 at 2-8°C

Upon receipt of supplies, a designated member of staff will conduct an inventory and acknowledge receipt to the supplier.

A record must be kept of all CN54ENV DNA and CN54gp140 used during the trial. This will include the description (lot numbers and expiry dates) and quantity of IMP received at the trial site and date of receipt, as well as a record of when (date of administration) and to whom (Trial ID) it was dispensed.

At the end of the trial, IMP accountability will be checked by the designated member of staff responsible for the inventory, and by the trial monitor. The Sponsor and the PI will retain copies of the complete IMP accountability.

All supplies (used and unused) will be retained at the trial site until the Sponsor gives instructions for their return or destruction.

6.1.3 Immunisation schedule

The doses, methods and schedule of immunisation are described in **Table 1** below.

Table 1: Schedule of Doses and Methods of Immunisation

Group	Method of immunization; Dose of DNA			Method of immunization; Dose of CN54gp140
	Dose 1 at WK 0	Dose 2 at WK 4	Dose 3 at WK 8	Dose 4 at WK 20
1 N=8	0.6mg ID*/ EP 2mg IM**	0.6mg ID*/ EP 2mg IM**	0.6mg ID*/ EP 2mg IM**	50ug ID***
2 N=8	0.6mg ID* 2mg IM**/ EP	0.6mg ID* 2mg IM**/ EP	0.6mg ID* 2mg IM**/ EP	50ug ID***
3 N=8	0.6mg ID*/ EP 2mg IM**/ EP	0.6mg ID*/ EP 2mg IM**/ EP	0.6mg ID*/ EP 2mg IM**/ EP	50ug ID***

* 1 x 0.15ml injections ID via a needle - into the upper arm with or without electroporation (EP).

** 1 x 0.5ml injections IM – into the upper thigh with or without electroporation (EP).

*** 1 x 0.1ml injections ID via a needle - into the upper arm.

6.1.4 Compliance and Adherence

All immunisations will be administered by site staff according to written procedures.

6.1.5 Dose Modifications and Discontinuation

There are no planned modifications to dose, other than discontinuation.

The schedule may be modified if a participant has symptoms or signs on the day of scheduled immunisation, and the investigator considers it best to defer the immunisation. The participant will be asked to return for review within the window period of the scheduled immunisations (-3/+7 days from week 4, 8 and 20 for the second, third and fourth immunisations respectively).

A clinical investigator may decide to permanently discontinue dosing in a participant who has received one or more immunisations, if the investigator deems that continuing might compromise participant wellbeing or interfere with the achievement of the trial's objectives. Such a decision should only be taken in consultation with the Chief Investigator. Participants will be encouraged to continue to attend trial visits for sampling and safety monitoring.

Discontinuation of dosing is essential following a grade 3 or 4 clinical or laboratory event (confirmed on examination or repeat testing respectively) which is considered possibly, probably or definitely related to the vaccine and which did not resolve within 72 hours.

Provided the participant agrees they will continue to be followed up for the duration of the study and samples will be collected at the allotted times.

Dosing must be discontinued in participants who become pregnant or HIV infected.

Participants may decide to discontinue dosing. They will be encouraged to provide a reason, and to remain in follow-up. The appropriate CRF should be completed as soon as possible if a patient chooses to stop receiving vaccines or to withdraw from the trial, and within 24 hours of a decision being taken to discontinue a participant when that decision is informed by an adverse event (**section 8.1**).

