6.3 Non-Trial Treatment

As stated in the exclusion criteria in **Section 4.2**, participants should not have received other immunisations, immunosuppressive agents, blood products, immunoglobulin or other trial medication within specified periods prior to enrolment. This applies during the trial through to the final safety visit 22 weeks after enrolment, 2 weeks after the last scheduled immunisation, unless the treatment is required for an emergency.

Should a participant require immunisation for the purposes of travel, occupation or other clinical need during the trial, the request will be reviewed by the Trial Management Group who will advise on timing and whether or not the trial immunisation schedule needs to be amended.

Participants will be allowed to continue with hormonal contraception if this forms part of their regular appropriate contraception plan. The precise method will be recorded on the screening CRF and any changes on the concomitant medication CRF.

All concomitant medication will be recorded on the CRF, including any dispensed by the investigators in the management of adverse events or reactions.

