7.5 Criteria for Stopping Treatment Groups or Whole Trial

In the event of a SUSAR, the Chief Investigator should notify the sponsor within 24 hours of the event taking place, and the Chief Investigator will arrange for any necessary expert reviews to take place within 3 working days.

Further immunisations will be put on hold until the review is completed.

A component of any expert review will be to consider whether or not further immunisations should be discontinued in the individual, and/or the trial.

If 3 or more participants experience a grade 3 or 4 clinical or laboratory event (confirmed on attendance or repeat testing) not resolved within 72 hours and considered possibly, probably or definitely related to vaccine product, further immunisations will be put on hold and the Chief Investigator will call a meeting with the Trial Management Group (TMG) to review the safety data. If upon review of the safety data it is deemed appropriate to restart dosing, a substantial amendment with relevant data has to be submitted to the MHRA for approval. If an unscheduled TMG meeting is warranted, the Sponsor will be informed and the TMG asked to make a recommendation to the Chief Investigator and the Sponsor about continuing further immunisations.

At any time if the study is put on hold (for example following the occurrence of a SUSAR) the Regulatory authority has to be informed of the temporary halt and a substantial amendment with relevant data has to be submitted to the MHRA for approval in case a

decision to resume dosing is taken. The Sponsor reserves the right to stop the whole trial at any time.

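### Section 6.1.5 does not require permanent discontinuation after a related anaphylaxis, laryngeal oedema, angio-oedema, bronchospasm or seizure that resolves within 72 hours

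*Protocol*

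**What the plan says.** **Stopping rule.** Section 6.1.5 requires discontinuation after a confirmed grade 3 or 4 clinical or laboratory event "considered possibly, probably or definitely related to the vaccine and which did not resolve within 72 hours". Its only other obligatory stops are pregnancy and HIV infection. Otherwise the investigator may stop dosing permanently, and "Such a decision should only be taken in consultation with the Chief Investigator". A dose may be deferred "if a participant has symptoms or signs on the day of scheduled immunisation".

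**Grading.** Under immediate reactions (onset within 6 hours), Appendix 2 puts anaphylactic shock at grade 4. Laryngeal oedema not needing intubation, asthma not needing admission, and angio-oedema are grade 3. Seizure has no row and is graded by the cited FDA guidance.

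**Reporting and review.** Section 8.2 lists as important adverse events any seizure, allergic bronchospasm needing intensive emergency care, and any event where intervention was needed to avert death or a threat to life. These must be reported within 24 hours on the SAE form and marked serious. Section 7.4.7 has the Principal Investigator review every serious event and the Trial Management Group discuss it, including whether to discontinue.

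**Holds.** After a SUSAR, section 7.5 says "Further immunisations will be put on hold until the review is completed". Expert review is arranged within 3 working days, and resuming needs an amendment approved by the MHRA. A separate hold applies when 3 or more participants have related, unresolved grade 3 or 4 events.

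**Entry.** Section 4.2 excludes people with "Known hypersensitivity to any component of the vaccine formulations used in this trial" (criterion 7), with a general vaccine reaction that includes "anaphylaxis; bronchospasm; laryngeal oedema; collapse; convulsions or encephalopathy within 72 hours" (criterion 8), or with "History of grand-mal epilepsy, seizure disorder or any history of prior seizure" (criterion 4).

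**The concern.** The 72-hour condition suits reactogenicity. Section 2.2.2.3 reports that electroporation site reactions usually settle in 24 to 72 hours and that transient grade 3 tenderness has occurred. It does not suit acute hypersensitivity or seizure, where quick recovery says nothing about whether the next dose of the same product is safe.

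The entry criteria already draw this distinction. In criterion 8, failure to resolve within 72 hours is a condition for local reactions only. For general reactions the 72 hours reads as the interval after vaccination in which the event occurs, and no minimum duration is set. Criteria 4 and 7 set none either. Someone known to be hypersensitive to a component cannot receive dose 1, while someone who shows it after dose 1 is not obliged to stop. Section 6.3 does carry the treatment-related exclusions forward ("This applies during the trial through to the final safety visit 22 weeks after enrolment"), but no text does so for criteria 4, 7 or 8.

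At stake is re-exposure of healthy volunteers who, by section 2.2.5, get no direct benefit.

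**Working it through.** This is mainly a reading of the rules against each other. There is no planned figure to reproduce except the Wilson limits in step 5.

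**1. Apply the mandatory stop.** It needs three things together: grade 3 or 4, related, and unresolved at 72 hours.

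| Related event, resolved within 72 h | Grade | Mandatory stop in 6.1.5 |
|---|---|---|
| Anaphylactic shock | 4 | No, duration condition fails |
| Laryngeal oedema, angio-oedema, asthma (Appendix 2 grade 3 forms) | 3 | No, duration condition fails |
| Seizure | Not in Appendix 2 | No, duration condition fails at any grade |

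**2. Look for another rule that forces the individual stop.**

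| Route | What must happen | Individual's permanent stop |
|---|---|---|
| SUSAR (7.5) | Hold, expert review, MHRA approval to resume; no 72-hour condition | To be considered |
| Serious or important event, not a SUSAR (8.2, 7.4.7) | 24-hour report marked serious, PI review, TMG discussion | To be considered |
| Neither serious nor important | Nothing specific | Investigator discretion, with the Chief Investigator (6.1.5) |
| 3 or more participants (7.5) | Hold, but with the same 72-hour condition | Not triggered |

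The third row is narrow: for example, grade 3 angio-oedema, or asthma needing neither admission nor intensive emergency care.

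**3. Does the deferral clause catch it?** It concerns symptoms on the dosing day. For an immediate reaction:
- latest end if resolved within 72 h: 6 h + 72 h = 78 h = 3.25 days;
- earliest next dose after dose 1 or 2 (section 7.1.2): 28 − 3 = day 25, so 25 − 3.25 = 21.75 days clear;
- after dose 3: 84 − 3 = day 81, so 81 − 3.25 = 77.75 days clear.

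The reaction is long over, so the clause does not reach it. A seizure with later onset could leave a shorter gap, but the clause would still depend on symptoms that day.

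**4. Doses remaining** (DNA at weeks 0, 4 and 8; protein at week 20):
- after dose 1: 3 (2 DNA, 1 protein);
- after dose 2: 2 (1 DNA, 1 protein);
- after dose 3: 1 (protein).

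**5. Cost of a forced stop.** The SAP per-protocol set (SAP 2.3) takes only randomised participants who received every dose, so one stop takes an arm from 8 to 7. The Wilson upper limit for zero events is z²/(n + z²), with z = 1.96 and z² = 3.84:
- n = 8: 3.84/11.84 = 32%;
- n = 7: 3.84/10.84 = 35%.

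Both match SAP Table 3.

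**The case against.** The strongest reply is that the plan surrounds these events with review. Section 8.2 routes any seizure, emergency-treated bronchospasm and life-threatening reaction into the serious pathway. The Chief Investigator then assesses SUSAR status, and the Sponsor has the final say on classification. The clinical experience in section 2.2.2.3 mentions none of these reactions, which points towards an unexpected event and hence the SUSAR hold. Adverse events are also assessed before each dose (Table 5), and section 9 gives a separate power to withdraw. In a single-site trial with at most 30 people exposed, relying on documented judgement could be called a drafting choice.

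Much of this stands. A reader might infer that, short of a SUSAR, nothing but investigator discretion precedes the next dose. The documents do not support that: section 8.2 and section 7.4.7 bring 24-hour reporting, PI review and group discussion for the most severe events. Nor do they show that anyone would in fact be redosed; the plan allows a stop at any time, and one is likely.

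Two things survive. No clause makes the individual stop automatic. And the protocol does not rely on judgement for prolonged grade 3 or 4 events: a related grade 3 laboratory change lasting four days forces a stop, while a related anaphylaxis treated within hours does not. That reverses the order of risk.

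It is also fair to object that a stop with no grade threshold would catch a mild wheeze with another equally good explanation. The fix is therefore tied to the Appendix 2 grades.

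**Conclusion.** The point holds as a gap in the mandatory rule, not as an absence of safeguards. A related anaphylaxis, laryngeal oedema, angio-oedema, bronchospasm or seizure that resolves within 72 hours does not oblige anyone to end that participant's dosing, with three, two or one doses still to come. It should be fixed, because the rule as written does not fit these reactions and correcting it costs little.

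The size is limited. The documents give no rate for these reactions, so I attach no probability; they are probably rare. No endpoint or analysis is affected.

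The conclusion assumes that important adverse events marked serious follow the review in section 7.4.7, as section 8.2 implies. Whether a given event is unexpected, and so a SUSAR, depends on the Investigator's Brochure. The Brochure and the site's written vaccination procedures were not available. Either could contain a contraindication to further dosing, but the protocol's own rule would still lack it.

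**What to change.** Add one sentence to section 6.1.5, by amendment:

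> Regardless of duration, dosing must also be permanently discontinued after anaphylaxis, after any other grade 3 or 4 immediate hypersensitivity reaction involving laryngeal oedema, angio-oedema or bronchospasm/asthma, or after any seizure, where the event is judged at least possibly related to the vaccine.

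Keep the 72-hour condition for every other grade 3 or 4 event, including local reactogenicity, laboratory changes, and isolated urticaria, pruritus or diarrhoea. Leave vasovagal events to judgement. Name seizure directly, since Appendix 2 does not grade it.

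The cost is a rare extra discontinuation, with the per-protocol loss shown in step 5. A replacement would not restore the SAP per-protocol set, because protocol section 10.4.1 defines replacements as non-randomised; the protocol's own per-protocol population does count them. The participant stays in the ITT and safety sets, and section 6.1.5 already provides for continued follow-up and sampling with the participant's agreement.
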